7.2 Viral Diagnostics

The NP swab on Days 0 and 3 will be tested by a central lab using a multiplex PCR for 22 respiratory pathogens and influenza types. The platform, Respifinder®, will be used according to manufacturer instructions. This multiplex PCR test can detect and differentiate 18 viruses (Coronavirus NL63, OC43, 229E, HKU1, Human metapneumovirus, Influenza A, Influenza A H1N1v, Influenza B, Parainfluenza 1 to 4, Respiratory syncytial virus (RSV) A and B, Rhinovirus/Enterovirus, Adenovirus, Bocavirus) as well as 4 bacteria (*Bordetella pertussis*, *Chlamydophila pneumoniae*, *Legionella pneumophila*, *Mycoplasma pneumoniae*).

7.3 Efficacy Evaluations

7.3.1 Diary Card for Fever, Symptoms, and Functional Assessment

Subjects will maintain a diary card, and will be asked to make a daily entry in the evening. On Day 0, subjects will be instructed on the diary card and the initial (baseline) assessment will be

completed by the subject and collected. The subject will make daily entries through Day 14. The subject completes the final diary card at the time of the final visit on Day 28 to represent end of study functional assessment and symptoms.

Completion of subsequent diary cards should be done by the subject if possible. For children unable to complete the card, it may be completed by a parent or close relative (and documented accordingly). For those subjects too ill to complete the diary card, it may be completed by the study team or treating team (physicians or nurses) and this will be documented accordingly.

At each subsequent study visit, the diary card for the day(s) since the last visit will be collected. This diary will contain the information listed below (Section 7.3.1.1 – 7.3.1.3).

7.3.1.1 Fever

Subjects will be asked to measure temperature orally at the time of completing the diary card and at any time they exhibit symptoms of feverishness, and will be asked to record the maximal temperature since the prior diary card).

7.3.1.2 Symptoms

Using a 4-point scale (0 = absent, 1 = mild, 2 = moderate, 3 = severe), each symptom will be assessed for severity.

The symptoms assessed are:

- Cough
- Sore throat
- Fatigue
- Headache
- Myalgia
- Rhinorrhea
- Nausea
- Vomiting
- Diarrhea
- Difficulty breathing/shortness of breath

7.3.1.3 Global Assessment

Subjects will be asked 2 global assessment questions:

- “Are you feeling as good as you did before you had the respiratory illness?” with a yes/no response, referring to the status immediately prior to onset of ILI symptoms.
- “Are you functioning as well as you were before you had the respiratory illness?” with a yes/no response, referring to the status immediately prior to onset of ILI symptoms.

Pediatric subjects that are not capable of answering the above questions will be assessed by a parent or close relative regarding:

- “Is your child as active as they were before they had the respiratory illness?” with a yes/no response, referring to the status immediately prior to onset of ILI symptoms.
- “Is your child eating as much as they were before they had the respiratory illness?” with a yes/no response, referring to the status immediately prior to onset of ILI symptoms.

7.3.2 Assessment for Presence of Complications

Subjects will be assessed for the signs/symptoms of the syndromes listed below, at baseline (Day 0) in order to know the presence of these prior to treatment, and on each study day to evaluate for the development of complications while participating in the study. In order to establish the listed diagnosis, the expected information to be in the source documentation follows each diagnosis in parentheses.

- Pneumonia (clinical diagnosis supported by radiographic data)
- Respiratory failure requiring mechanical ventilation (documentation of mechanical ventilation)
- ARDS (clinical diagnosis supported by radiographic data)
- Sepsis (clinical diagnosis)
- Bronchiolitis (clinical diagnosis)

7.3.3 Vital Signs, Including SaO₂

Vital signs assessments (temperature, blood pressure, pulse, respiration rate, and SaO₂) will be taken on Study Days 0, 3, 7, and 28. SaO₂ will be measured by clinically available transcutaneous pulse-oximeters.

7.4 Compliance Measures

Treatment compliance will be assessed by examination of subject's remaining study product at each study visit, and by asking subjects to document study drug compliance on the diary cards. No pharmacokinetics or other drug exposure testing is planned for this study.

7.5 Severity of Illness Scores

7.5.1 SOFA Score

The SOFA score is a scoring system to determine the extent of a person's organ function or rate of failure^{15, 16} and is based on 6 different scores, one each for the respiratory, cardiovascular, hepatic, coagulation, renal, and neurological systems.

Respiratory System

PaO₂/FiO₂ (mmHg)

- ≥ 400 , 0 points
- < 400 , 1 point
- < 300 , 2 points
- < 200 and mechanically ventilated, 3 points
- < 100 and mechanically ventilated, 4 points

If PaO₂ is not available, the following table can be used to generate the SOFA score with SaO₂¹⁷:

Table 7: Sofa Score

SpO ₂ /FiO ₂ Ratio				
SOFA Score	PaO ₂ /FiO ₂ Ratio	PEEP< 8 or not intubated	PEEP 8-12	PEEP>12
0	≥ 400	≥ 457	≥ 515	≥ 425
1	< 400	< 457	< 515	< 425
2	< 300	< 370	< 387	< 332
3	< 200	< 240	< 259	< 234
4	< 100	< 115	< 130	< 129

Note: The original SpO₂/FiO₂ Ratio as published would require a SaO₂ > 110% to achieve a SOFA score of 0. Therefore, this score has been modified to accept a SaO₂ of 96% or greater on room air as normal (i.e. a SpO₂/FiO₂ Ratio of ≥ 457 would be a SOFA score = 0).

Nervous System

Glasgow coma score

- 15, 0 points
- 13 – 14, 1 point
- 10 – 12, 2 points
- 6 – 9, 3 points
- < 6, 4 points

Cardiovascular System

Mean arterial pressure OR administration of vasopressors required (vasopressor drug doses are in mcg/kg/min)

- No hypotension, 0 points
- MAP < 70 mm/Hg, 1 point

- dopamine \leq 5 or dobutamine (any dose), 2 points
- dopamine $>$ 5 OR epinephrine \leq 0.1 OR norepinephrine \leq 0.1, 3 points
- dopamine $>$ 15 OR epinephrine $>$ 0.1 OR norepinephrine $>$ 0.1, 4 points

Liver

Total Bilirubin (mg/dL)

- <1.2 , 0 points
- $1.2 - 1.9$, 1 point
- $2.0 - 5.9$, 2 points
- $6.0 - 11.9$, 3 points
- > 12.0 , 4 points

CoagulationPlatelets $\times 10^3/\mu\text{L}$

- ≥ 150 , 0 points
- < 150 , 1 point
- < 100 , 2 points
- < 50 , 3 points
- < 20 , 4 points

Renal System

Creatinine (mg/dL) (or urine output)

- <1.2 , 0 points
- $1.2 - 1.9$, 1 point
- $2.0 - 3.4$, 2 points
- $3.5 - 4.9$ (or $< 500 \text{ mL/d}$), 3 points
- ≥ 5.0 (or $< 200 \text{ mL/d}$) or dialysis requirement, 4 points

7.5.2 Tal Bronchiolitis Score

The modified Tal bronchiolitis score should be used for all children < 24 months of age at the time of enrollment.¹⁸ Each of 4 categories are evaluated, and assigned a score of 0-3 per category (total score will be 0-12).

Table 8: Tal Bronchiolitis Score

Score	Respiratory Rate (per min)	Wheezing	Cyanosis	Accessory muscle use
0	30	None	None	None
1	31-45	End expiration with stethoscope	Perioral with crying	+
2	46-60	Inspiration and expiration with stethoscope	Perioral at rest	++
3	> 60	Audible without stethoscope	Generalized at rest	+++

8 ASSESSMENT OF SAFETY

8.1 Definitions

Adverse Event (AE)

An AE is any untoward or unfavorable medical occurrence in a human subject, including any abnormal sign (e.g., abnormal physical exam or laboratory finding), symptom, or disease, temporally associated with the subject's participation in the research, whether or not it is considered related to the research.

Adverse Reaction (AR)

An AE that is caused by an investigational agent (drug or biologic)

Suspected Adverse Reaction (SAR)

An AE for which there is a reasonable possibility that the investigational agent caused the AE. 'Reasonable possibility' means that there is evidence to suggest a causal relationship between the drug and the AE. A suspected adverse reaction implies a lesser degree of certainty about causality than an adverse reaction which implies a high degree of certainty.

Serious Adverse Event (SAE)

A SAE is an AE that results in 1 or more of the following outcomes:

- death
- a life threatening (i.e., an immediate threat to life) event
- an inpatient hospitalization or prolongation of an existing hospitalization
- a persistent or significant incapacity or substantial disruption of the ability to conduct normal life functions
- a congenital anomaly/birth defect
- a medically important event*

** Medical and scientific judgment should be exercised in deciding whether expedited reporting is appropriate in other situations, such as important medical events that may not be immediately life threatening or result in death or hospitalization but that may jeopardize the subject or may require intervention to prevent 1 of the other outcomes listed above.*

Unexpected Adverse Event

An AE is unexpected if it is not listed in the IB or Package Insert (for marketed products) or is not listed at the specificity or severity that has been observed. It is the responsibility of the IND Sponsor to make this determination.

Serious and Unexpected Suspected Adverse Reaction (SUSAR)

A SUSAR is a Suspected Adverse Reaction that is both Serious and Unexpected.

Unanticipated Problem (UP)

An Unanticipated Problem is any event, incident, experience, or outcome that is

1. unexpected in terms of nature, severity, or frequency in relation to

- a. the research risks that are described in the IRB-approved research protocol and informed consent document; Investigator's Brochure or other study documents; and
- b. the characteristics of the subject population being studied; and
2. possibly, probably, or definitely related to participation in the research; and
3. places subjects or others at a greater risk of harm (including physical, psychological, economic, or social harm) than was previously known or recognized. (Per the IND Sponsor, an AE with a serious outcome will be considered increased risk.)

Unanticipated Problem that is not an Adverse Event (UPnonAE)

An incident, experience or outcome that is not associated with an AE which meets the 3 criteria of a UP. Examples include occurrences of breaches of confidentiality, accidental destruction of study records, and unaccounted-for study drug.

Protocol Violation

A Protocol Violation is any change, divergence, or departure from the study design or procedures in an IRB-approved research protocol that has a major impact on the subject's rights, safety, or well-being and/or the completeness, accuracy or reliability of the study data.

Protocol Deviation

A Protocol Deviation is any change, divergence, or departure from the study design or procedures of an IRB-approved research protocol that does not have a major impact on the subject's rights, safety or well-being, and/or the completeness, accuracy and reliability of the study data.

8.2 Investigator Assessment of Adverse Events

8.2.1 Determination of Adverse Event

All worsening symptoms should be evaluated as potential adverse events:

- If a diagnosis is clinically evident (or subsequently determined), the diagnosis, rather than the individual signs and symptoms or lab abnormalities, will be recorded as the AE.
- Gastrointestinal tract SARI symptoms such as nausea, vomiting, or diarrhea, can be either related to SARI or the study drug. For this reason, if these gastrointestinal symptoms are new from baseline or worsen, they should be graded per the DAIDS toxicity table, and if they are new or represent a worsening grade then they should be reported as adverse events.
- Upper respiratory tract SARI symptoms (such as cough, sore throat, fatigue, headache, myalgia, rhinorrhea) can worsen due to the underlying disease. As these are unlikely to be related to the study drug, these do not need to be reported as Adverse Events.
- Any other new symptoms should be recorded as AEs.
- Symptoms present at baseline that resolve should have an end date (unless likely flu related). If they recur, the recurrence should be reported as an adverse event. Intermittent symptoms (such as cough, headache, rhinorrhea) would not be AEs if likely influenza related.

All worsening laboratory values should be evaluated as potential adverse events:

- If an abnormal laboratory finding is captured as a component of a diagnosis AE term that has already been recorded as a pre-study condition, the individual abnormal laboratory finding is **NOT** recorded as a separate AE.
- A laboratory abnormality should be reported as an AE only **if** it requires an intervention. Interventions include, but are not limited to, discontinuation of treatment, dose reduction/delay, additional assessments (including additional lab assessments), or concomitant treatment.
- In addition, any medically important laboratory abnormality may be reported as an AE at the discretion of the investigator who considers the test result clinically significant. This could include a laboratory result for which there is no intervention but the abnormal value is of clinical concern or suggests disease or organ toxicity. Grading should be based on the toxicity table where applicable.

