1.4 Risks and Benefits

1.4.1 Risks of NTZ

NTZ has been marketed in the United States since 2003 and in Latin America since 1996. It is estimated that more than 50 million patients have been exposed to NTZ post-marketing worldwide. No drug-related serious adverse events (SAEs) have been reported during post-marketing experience with NTZ.

Phase 2 and 3 clinical studies have been conducted in approximately 4,000 patients to evaluate the safety and efficacy of NTZ in treating parasitic, bacterial, and viral infections. During these studies, no drug-related SAEs were observed. The side effects have been usually of a mild transient nature, and less than 1% of patients have discontinued therapy because of an AE. The most common AEs reported in clinical trials include abdominal pain, diarrhea, headache, nausea, and vomiting and did not differ significantly from those of placebo. Clinical chemistry and hematology obtained before and after treatment have not revealed any abnormalities attributable to the test drug.

Nitazoxanide is US FDA Pregnancy Category B: No impaired fertility or harm to the fetus in animal studies was noted, but there are no adequate and well-controlled studies in pregnant women.

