2.2 Secondary Objectives

1. Evaluate the clinical efficacy of NTZ + SOC vs. PCB + SOC with regards to:
 - Percent hospitalized at Study Day 3, 7, 14 and 28
 - Death by Study Day 28
 - Duration of clinical symptoms (defined in Section 7.3.1.2)
 - Duration of fever
 - Use of supplemental oxygen (or increase greater than baseline oxygen requirement)
 - Admission to ICU
 - Intubation/mechanical ventilation
 - Proportion of subjects who develop complications including pneumonia, respiratory failure requiring mechanical ventilation, acute respiratory distress syndrome (ARDS), sepsis, or bronchiolitis.
 - Time to resumption of normal activity
 - Antibiotic/antiviral use during hospitalization
 - Systemic corticosteroid use during hospitalization
 - Re-hospitalization within 28 days
2. Evaluate the virologic efficacy of NTZ + SOC vs. PCB + SOC with regards to:
 - Percent cessation of viral shedding at Study Day 3
3. Evaluate the safety and tolerability of NTZ assessed by:
 - Cumulative incidence and severity of AEs
 - Cumulative incidence of SAEs
 - Cumulative incidence of laboratory abnormalities on Study Days 3, 7 and 28

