## 9. Adverse Events (ITT)

- Table: [14.3.1.1] Number (%) of subjects with an AE by MedDRA System Organ Class (SOC) and Preferred Term (PT) and severity grade; number (%) of subjects with any AE. In this table, subjects with AEs will be counted (e.g. counting a subject with multiple AEs with the same PT only once for that PT).
- Table: [14.3.1.2] Number of AEs by MedDRA System Organ Class (SOC) and Preferred Term (PT) and severity grade; number (%) of AEs. In this table, AEs will be counted (e.g. counting multiple AEs with the same PT within the same subject).
- List of AEs: Randomized arm, days from randomization to first AE experienced by a subject, subject ID, site, age, days from start of study drug to AE, AE (MedDRA SOC and PT, and verbatim description), severity grade, relatedness to study intervention, outcome (sort by randomized arm, subject ID, MedDRA SOC and PT and, if a subject has multiple AEs, days from randomization to AE). This listing will include any AE that occur after day 28 and are reported.
- Listing of AE after enrollment (informed consent) and not included in the ITT

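### Worsening headache is exempt from AE reporting although the protocol names headache among the common NTZ AEs, so the AE tables will under-count it by an unknown amount and no planned analysis compensates

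*Protocol*

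**What the plan says.** Protocol 8.2.1 gives separate reporting rules for two groups of disease symptoms.

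- For the gut symptoms it says: "Gastrointestinal tract SARI symptoms such as nausea, vomiting, or diarrhea, can be either related to SARI or the study drug". If new or worse than baseline, they are graded on the DAIDS table and reported.
- For the second group it says: "Upper respiratory tract SARI symptoms (such as cough, sore throat, fatigue, headache, myalgia, rhinorrhea) can worsen due to the underlying disease". It continues: "As these are unlikely to be related to the study drug, these do not need to be reported as Adverse Events". No severity threshold is attached.

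A later bullet in 8.2.1 makes recurrence of a resolved baseline symptom reportable, then adds: "Intermittent symptoms (such as cough, headache, rhinorrhea) would not be AEs if likely influenza related".

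Protocol 1.4.1 describes the drug's AE profile: "The most common AEs reported in clinical trials include abdominal pain, diarrhea, headache, nausea, and vomiting", and says that these "did not differ significantly from those of placebo".

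The safety objective in Protocol 2.2 includes "Cumulative incidence and severity of AEs". SAP section 9 serves it with tables by arm, among them "Number (%) of subjects with an AE by MedDRA System Organ Class (SOC) and Preferred Term (PT) and severity grade".

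Protocol 7.3.1 and 7.3.1.2 have each subject score headache from 0 to 3 on a daily diary through Day 14 and again on Day 28.

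**The concern.** Headache is the one symptom on the 1.4.1 list that 8.2.1 puts in the exempt group. A headache that is mild at baseline and becomes severe during dosing, without first resolving, need not be reported as an AE unless it meets an SAE criterion. No reason is given for handling it differently from nausea, vomiting and diarrhea, which may equally come from the illness or the drug.

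What is at stake is the by-arm comparison of AE incidence and severity for a symptom that the protocol itself names as common under NTZ. Protocol 1.2.5 says there are no NTZ data in hospitalized influenza or ILI, so this trial would be the first source. The randomized, blinded placebo arm already separates drug effect from disease course, provided that the events are counted. AE reports also feed the protocol team's periodic safety review (8.7.2).

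**Working it through.** No figure in the documents is in dispute. The check is a comparison of sections, followed by an illustration under stated assumptions.

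**1. The five AEs named in 1.4.1 against the rules in 8.2.1**

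| AE named in 1.4.1 | Rule in 8.2.1 |
|---|---|
| Nausea | Grade; report if new or worse |
| Vomiting | Grade; report if new or worse |
| Diarrhea | Grade; report if new or worse |
| Abdominal pain | Not named; falls under other new symptoms, which are recorded |
| Headache | Need not be reported when it worsens |

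One of the five is exempt. The statement that these AEs were similar to placebo covers all five, so it cannot explain why only one is exempt.

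**2. What the other rules catch**

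- Recurrence of a resolved headache is reportable, but the same bullet removes intermittent headache judged likely to be influenza related.
- New-onset headache is unclear. The gut rule covers new and worsening symptoms. The exempt-group rule speaks of worsening. The catch-all covers only other new symptoms. Sites may read this differently.
- A headache meeting an SAE criterion is reported.
- Continuous worsening short of an SAE is left to the site.

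**3. What the SAP does with the diary**

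Headache appears in the baseline table (SAP section 3). After baseline it enters only the duration of clinical symptoms (SAP section 12), where symptom free means a score of 0 or 1 on every symptom for at least 2 days. That composite misses a rise from 0 to 1 and a rise from 2 to 3. It does not register a headache that worsens while cough still scores 2 or more, nor one that starts after the 2-day criterion has been met. No by-arm headache summary is planned.

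**4. Illustration of the loss**

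Inputs: n = 145 per arm (290 randomized 1:1, Protocol 3.4). The true headache rates p0 and p1, and the share r of headaches reported as AEs (the same in both arms), are assumptions. The SAP plans no test on AE counts; power is used only to gauge how far the arms could be told apart.

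With a = r·p0, b = r·p1 and m = (a + b)/2, at two-sided 0.05:

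power = Φ{ [ |b − a| − 1.96·√(2m(1 − m)/n) ] / √([a(1 − a) + b(1 − b)]/n) }

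For 5% and 15%:

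- r = 1: (0.10 − 1.96 × 0.03523)/0.03474 = 0.89, so power is 81.3%.
- r = 0.5: (0.05 − 1.96 × 0.02560)/0.02543 = −0.01, so power is 49.7%.

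| Assumed true rates | r = 1 | r = 0.5 | r = 0.25 |
|---|---|---|---|
| 5% and 15% | 81.3% | 49.7% | 27.5% |
| 10% and 20% | 66.6% | 36.5% | 20.0% |
| 10% and 25% | 92.4% | 61.9% | 34.4% |

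Equal under-reporting shrinks the observed difference in proportion to r. It removes the difference only if no headache at all is reported.

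**The case against.** The strongest reply has four parts.

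- Section 1.4.1 says the common AEs were similar to placebo, so listing headache there and calling it unlikely to be drug related in 8.2.1 are compatible. This stands in part: the documents do not establish headache as a drug reaction. It does not justify the split, because the same statement covers nausea, vomiting and diarrhea, which are reported.
- The exemption is permissive. Section 8.2.1 opens by asking that all worsening symptoms be evaluated as potential AEs, some recurrences are reportable, and reporting headache is never forbidden. This stands. It means the under-count is partial and of unknown size, and it leaves reporting to site habit.
- Headache is recorded elsewhere: daily in the blinded diary, indirectly through concomitant medication (5.7), and through the reason for stopping study drug (4.6). This stands as to data collection. None of these routes leads to a planned by-arm headache comparison.
- Headache is a qualifying symptom for enrollment (4.3) and the gut symptoms are not, so there is some reason to treat it as expected disease. That explains how the list may have arisen. In a placebo-controlled trial it is not a reason to leave the event uncounted, and 8.1 defines an AE regardless of relatedness.

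**Conclusion.** Sections 1.4.1 and 8.2.1 treat symptoms from one list unequally without a stated reason. The AE tables will under-count headache in both arms, and the SAP has no analysis that makes up for it. The change should be made, but the primary endpoint is not affected.

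The size cannot be fixed from the documents. The power figures rest on assumed rates, an assumed reporting share equal in both arms, and 145 subjects per arm.

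A reader might infer more than the documents support:

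- That the trial cannot detect a headache effect, or that reported headache will be close to zero. Reporting is waived rather than barred, and the diary data exist.
- That a site would not record a worsening headache. The diary would show it; what may be missing is the AE report.
- That headache is a known reaction to NTZ. Section 1.4.1 calls it a common AE, not significantly different from placebo.

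**What to change.** 1. In Protocol 8.2.1, reconcile the text with 1.4.1 by moving headache to the rule already used for nausea, vomiting and diarrhea: grade it on the DAIDS table, and report it if it is new from baseline or a worsening grade. Align the bullet on intermittent symptoms, which also names headache.

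2. Before unblinding, add to SAP section 9 one table by arm: the number (%) of subjects whose diary headache score rose above their Day 0 score during Days 1–5 and during Days 1–14, by maximum diary score. Label it as the 0–3 diary scale, not the DAIDS grade. Use as denominator the subjects with a Day 0 score and at least one later score in the window, and state how many started at 3 and so could not rise.

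The table uses data already collected, so it also covers subjects enrolled before the reporting rule changes. The cost is a short protocol edit, one table and some additional low-grade AE entries.
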